9.3.4 Subject Identification and Replacement of Subjects

Each subject will be assigned a unique subject identifier. This unique identifier will be on all CRF pages. In legal jurisdictions where use of initials is not permitted, a substitute identifier will be used.

Subjects who withdraw from the study will not be replaced.

9.3.5 Duration of Subject Participation

The duration of this study will be approximately 264 weeks. This includes 4 weeks of screening, 1 day of BMN 270 infusion, 16 weeks of Post-Infusion Follow-Up, and 244 weeks of Safety Follow-Up. A primary endpoint analysis on safety and efficacy will be performed at 16 weeks.

9.4 Treatments

BioMarin or its designee will provide the study site with study drug sufficient for study completion. BioMarin is responsible for shipping study drug to clinical sites.

9.4.1 Treatments Administered

BioMarin and/or its designee will provide the study site with a supply of IP sufficient for the completion of the study.

BOMARIN	270-201 – Amendment 5	Page 48
---------	-----------------------	---------

9.4.2 Identity of Investigational Product

9.4.2.1 Product Characteristics and Labeling

BMN 270 is a sterile, clear, colorless-to-pale yellow solution for IV infusion and is supplied in a 2 mL polypropylene cryovial. Each vial contains 1.1 mL of AAV5-hFVIII-SQ at a concentration of 2E13 vector genomes per mL in a pH 7.4 phosphate buffer.

The study drug label includes the following information: lot number, required storage conditions, a precautionary statement, expiry date, study number, and BioMarin name and address. Labelling will be done according to country specific requirements.

9.4.3 Storage

At the study site, all IP must be stored under the conditions specified in the IB in a secure area accessible only to the designated pharmacists and clinical site personnel. All IP must be stored and inventoried and the inventories must be carefully and accurately documented according to applicable state, federal and local regulations, ICH GCP, and study procedures.

9.4.4 Directions for Administration

After a physical examination performed by the PI or designee, participants will be admitted on the day of BMN 270 infusion. An IV catheter will be inserted into a suitable peripheral vein (e.g. the median cubital vein) and flushed with saline. FVIII replacement therapy will not be given since venipuncture is a minimally invasive procedure in these individuals under ordinary conditions.

BMN 270 will be prepared and infused as a pure solution over a dose-dependent time. Prepared drug will be kept at room temperature prior to administration. An electric syringe pump will be used to infuse through an in-line, low protein binding 0.22 micron filter. BMN 270 will be infused through the catheter using an appropriate infusion pump at a constant rate of 4 ml/min while monitoring the vital signs (pulse, blood pressure, respiration rate and temperature) at 15 minute (\pm 5 minutes) intervals. The anticipated maximum interval from initiation of thawing of BMN 270 to completion of the infusion is 4 hours, although the IP has been shown to be stable at room temperature for 6 hours.

Following completion of the infusion, vital signs will be monitored hourly (\pm 5 minutes) for 6 hours and then every 2 hours (\pm 15 minutes) for 6 hours and then at 4 hour intervals. If the vital signs are stable the catheter will be removed 20-24 hours after the infusion. Hemostasis at the puncture site will be established by applying pressure according to standard protocol for infusing FVIII concentrates. Subjects will remain in the clinic for 24 hours to observe for any immediate toxicity of the procedure. After 24 hours, participants will be

BIOMARIN	270-201 – Amendment 5	Page 49
----------	-----------------------	---------

discharged from the clinic unless toxicity has been observed in which case the stay in the clinic may be extended or the subject may transfer to a separate facility based on the evaluation and judgment of the Principal Investigator after consultation with the Medical Monitor.

9.4.5 Method of Assigning Subjects to Treatment Groups

Subjects who meet all eligibility criteria (refer to Section 9.3.1 and Section 9.3.2) may be enrolled into the study. Approval by the Sponsor will be required prior to enrollment of each study subject. Upon their enrollment into the study, subjects will be assigned a unique subject number and dose level by the Sponsor.

Cohorts 1 to 3 are enrolled serially and their dose is defined in Section 9.4.6.2 below. Escalation is based on FVIII activity 3 weeks after injection. Cohorts may receive the next higher dose if subjects in the previous cohort does not meet the activity criteria, or the same dose if subjects in the previous cohort meets the activity criteria. Subjects in Cohort 4 will all be enrolled at a single dose.

9.4.6 Selection of Doses Used in the Study

The starting dose was based on the expression of hFVIII observed in nonclinical studies of mice and monkeys. The starting dose has a significant safety margin (10-fold) from NOAEL in mice. The dose escalation is half-logs based.

9.4.6.1 Selection of Timing of Dose for Each Subject

A minimum of three weeks are required between subjects, to allow for evaluation of safety and expression of hFVIII. After three weeks, depending on the activity level, the choice of the dose for the next subject will be made as described below.

9.4.6.2 Selection of Dose for Each Subject

The starting dose was determined by expression of hFVIII observed in mice and monkeys and a scale up factor based on previous experience, an improved purification process over previous trials (thus potentially decreasing the risk of immune response), and a new evaluation of the titer (PCR performed after hairpin removal).

For Cohorts 1 to 3, approximately three weeks after an injection, the decision to escalate to the next dose level will be made based on the review of safety parameters and FVIII activity by the Sponsor and the DRB.

Subject 1 (Cohort 1) will be dosed by intravenous infusion with 6E12 vg/kg of body weight. If the FVIII activity level does not reach 5 IU/dL or greater (expressed as % in Figure 9.1.1)

BOMARIN	270-201 – Amendment 5	Page 50
---------	-----------------------	---------

at the Week 3 visit in both assays, then no further subjects will be dosed in Cohort 1 and enrollment into Cohort 2 will initiate with Subject 2 at the next dose (2E13 vg/kg).

If the FVIII activity level in the first subject treated in Cohort 2 does not reach \geq 5 IU/dL at the Week 3 visit in both assays, then no further subjects will be dosed in Cohort 2 and enrollment into Cohort 3 (6E13) will initiate with the next subject.

If the FVIII activity level in the first subject treated in Cohort 3 does not reach \geq 5 IU/dL at the Week 3 visit in both assays, then the DRB will recommend whether to continue to add subjects to the cohort and/or whether to continue the study.

For the first subject treated in each of the first 3 cohorts, if the activity level reaches ≥ 5 IU/dL and no safety issue is found, then up to four subjects will be enrolled in that cohort, though the adaptive nature of this trial allows the DRB to recommend allocating subjects to the cohorts based on activity levels of FVIII and safety signals.

For Cohort 4, 3 subjects will be enrolled at 4E13 vg/kg. If FVIII activity in these 3 subjects is \geq 5% at 8 weeks and if no safety issue is found, an additional 3 subjects may be enrolled in this cohort.

There will be an ongoing review of individual patient safety and efficacy data by the medical monitor and the DRB. The adaptive nature of this trial allows the DRB to recommend allocating subjects to the cohorts based on activity levels of FVIII and safety signals.

Refer to Figure 9.1.1 for a visual representation of the study design for Cohorts 1-3

9.4.7 Blinding

This is an open-label study.

9.4.8 Prior and Concomitant Medications

All prescription and over-the-counter medications (including dietary and herbal supplements) taken by a subject for 30 days before Screening will be recorded on the designated CRF. The Investigator may prescribe additional medications during the study, as long as the prescribed medication is not prohibited by the protocol. In the event of an emergency, any needed medications may be prescribed without prior approval, but the medical monitor must be notified of the use of any contraindicated medications immediately thereafter. Any concomitant medications added or discontinued during the study should be recorded on the CRF.

BOMARIN	270-201 – Amendment 5	Page 51
---------	-----------------------	---------

The following medications are prohibited starting 30 days before Screening:

- Live vaccines
- Systemic immunosuppressive agents

Medications which are predominately metabolized by the liver (e.g., acetaminophen) and alcohol should, whenever possible, be avoided for the first 52 weeks of the study, and particularly within 48 hours prior to lab work.

9.4.8.1 Concomitant Haemophilia Treatments

Subjects on "on demand" therapy for FVIII will continue their treatment at will. Subjects on prophylactic FVIII therapy will discontinue their treatment starting the day of infusion and switch to an "on demand" schedule. FVIII can always be taken as needed by the subject, who will carefully record his treatment and bleeding episodes in his diary. In addition, information on FVIII usage by medical history will be collected (if available) from subjects for the 6 month period immediately preceding study enrollment.

9.4.8.2 Glucocorticoid Treatment of Elevated Hepatic Transaminases

During the Post-Infusion Follow-up Period and the Safety Follow-Up Period, each subject will have comprehensive surveillance plan monitoring of LFTs (at local labs, once per week for Weeks 1-36, then once every 2 weeks from Week 37-52). LFTs may be monitored more or less frequently (and in particular when ALT values are >1.5x ULN) based on discussion between the Medical Monitor and the Investigator and review of subject data.

9.4.8.2.1 Therapeutic Corticosteroids

In general, therapeutic corticosteroids may be initiated when a subject's ALT value is $\geq 1.5x$ ULN, or based on review of FVIII and liver enzyme data after consultation between the Medical Monitor and the Investigator.

Reports of raised LFTs (defined as $ALT \ge 1.5x$ ULN) should be made to the BioMarin medical monitor within 30 minutes of the lab value being available. Local laboratory results of LFTs will be used to trigger corticosteroid treatment as needed. In case of discrepant results between local and central laboratories, the Investigator and Medical Monitor will decide further action.

Following initiation or completion of therapeutic corticosteroids, if ALT elevation $\geq 1.5x$ ULN is reported, steroid management decisions will based on discussions between the Investigator and Medical Monitor. Modification of the steroid regimen may take into consideration possible confounders for the ALT elevation and impact on FVIII expression.

BOMARIN	270-201 - Amendment 5	Page 52
---------	-----------------------	---------

Treatment with prednisolone will be initiated at a dose of 60 mg per day and then gradually tapered (60 mg daily for the first 2 weeks, then 40 mg the next 2 weeks, then 30 mg the next two weeks, then 20 mg the next two weeks, then 15 mg for the next week, then 10 mg for the next week, then 5 mg for the next week, then stop, for a total treatment of 11 weeks) (refer to Table 9.1.5).

After discontinuation of corticosteroids, weekly labs for ALT and FVIII levels will be measured once a week for 4 weeks to ensure stability in values.

Management and monitoring of reactions to corticosteroids should be determined by the Investigator's clinical judgment in consultation with the Sponsor's Medical Monitor. This includes the contraindicated use of NSAIDs during corticosteroid treatment, and specific monitoring not already covered by the schedule of events. Hepatitis B status and HCV viral load will be rechecked 6 weeks after the start of corticosteroid treatment, and then 1 week and 13 weeks after the completion of corticosteroid treatment. All adverse events should be reported as outlined in Section 10 of the protocol.

9.4.9 Treatment Compliance

Study drug will be administered to subjects at the study site by a qualified professional. The quantity dispensed, returned, used, lost, etc. must be recorded on the dispensing log provided for the study. Sites will be instructed to return or destroy all used and unused study drug containers.

9.5 Investigational Product Accountability

The Investigator or designee is responsible for maintaining accurate records (including dates and quantities) of IP(s) received and IP lost or accidentally or deliberately destroyed. The Investigator or designee must retain all unused or expired study supplies until the study monitor (on-site CRA) has confirmed the accountability data.

9.5.1 Return and Disposition of Clinical Supplies

Unused study drug must be kept in a secure location for accountability and reconciliation by the study monitor. The Investigator or designee must provide an explanation for any destroyed or missing study drug or study materials.

Unused study drug may be destroyed on site, per the site's standard operating procedures, but only after BioMarin has granted approval for drug destruction. The monitor must account for all study drug in a formal reconciliation process prior to study drug destruction. All study drug destroyed on site must be documented. Documentation must be provided to BioMarin and retained in the Investigator study files. If a site is unable to destroy study drug

BOMARIN	270-201 – Amendment 5	Page 53
---------	-----------------------	---------

appropriately, the site can return unused study drug to BioMarin upon request. The return of study drug or study drug materials must be accounted for on a Study Drug Return Form provided by BioMarin.

All study drug and related materials should be stored, inventoried, reconciled, and destroyed or returned according to applicable state and federal regulations and study procedures.

9.6 Dietary or Other Protocol Restrictions

There are no dietary or other protocol restrictions for this study.

9.7 Safety and Efficacy Variables

As this is a first-in-man study, the primary endpoint of safety will be assessed as explained in Section 9.7.8.

The primary efficacy measure will be to assess plasma FVIII activity. The efficacy goal of the study is to establish the dose relationship to FVIII activity \geq 5 IU/dL at 16 weeks post BMN 270 administration.

9.7.1 Safety and Efficacy Measurements Assessed

The Schedule of Events (Table 9.1.1 through Table 9.1.4) describes the timing of required evaluations.

9.7.2 Primary Efficacy Variables

The primary efficacy measure will be the plasma FVIII activity monitored on a regular basis after BMN 270 dose. The efficacy goal of the protocol is to ascertain the dose range of BMN 270 required to convert severe HA patients to expression of FVIII at 5 IU/dL or above, i.e., a mild severity. This is associated in natural history studies with clinically superior long term outcomes (Den Ujil, 2011, Haemophilia).

The following assays (assessed by the central laboratory) will be used to measure the primary efficacy variable:

- FVIII activity (chromogenic FXa assay)
- FVIII activity by one-stage APTT (Activated Partial Thromboplastin Time)

If a subject has used FVIII within 72 hours of a measurement day, all efforts should be made to obtain FVIII activity measurements when a 72-hour interval without FVIII use is achieved.

The FVIII activity level in both assays and the number of subjects with FVIII activity ≥ 5 IU/dL in at least one of the two assays will be summarized.

BOMARIN	270-201 – Amendment 5	Page 54
---------	-----------------------	---------

FVIII activity assays will also be performed at the local laboratory at the time points indicated in Table 9.1.2, Table 9.1.3, and Table 9.1.4, but will be used in conjunction with local lab LFT assessments to monitor subject safety and need for initiation of therapeutic corticosteroid dosing; local laboratory FVIII activity assessments will not be used to assess efficacy or to measure the primary efficacy outcome of the study.

Timing of assessment by these assays is provided in Table 9.1.2, Table 9.1.3, and Table 9.1.4. Details on performing the assays are included in the Laboratory Manual.

9.7.3 Secondary Efficacy Variables

Secondary efficacy measures will be the reduction in the frequency of factor replacement therapy, and reduction in the number of bleeding episodes. Subjects will be asked at each study visit to report the use of factor replacement therapy and the number of bleeding episodes since the previous visit. This information will be captured on the subject's diary or other subject records.

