Treatment of severe HA presently consists of intravenous injection of plasma derived or recombinant human FVIII protein (rhFVIII) concentrates both as prophylaxis 2-4 times per week, and at the time of a bleed, to prevent or control bleeding episodes, respectively. The half-life for FVIII (12-18 hours for most approved products) necessitates frequent infusions, and although a major advance in the treatment of HA, it remains common for severe HA patients to continue to have multiple bleeding events on treatment (mean of 1 to 7 episodes/year with prophylaxis and up to 30 to 50 episodes/year for on demand treatment) (Nagel, 2011, Haemophilia.). The consequence of multiple bleeding events is the development of an underlying pathology that contributes to debilitating multiple-joint arthropathy and substantially increased risk of death (Nagel, 2011, Haemophilia). Chemical modification (e.g. direct conjugation of polyethylene glycol (PEG) polymers) and bioengineering of FVIII (e.g. FVIII-Fc fusion proteins) improve half-life by approximately 50%, and thus, show promise in reduced dosing and maintaining activity levels above 1%trough (Stonebraker, 2010, Haemophilia.), (Mahlangu, 2014, Blood). However, these longer acting FVIIIs remain dependent on multiple infusions to maintain critical levels of FVIII activity in severe HA patients. There is therefore a strong unmet need for a fully preventive treatment of HA to give patients a FVIII level compatible with a normal and haemorrhage-free life.

Proprietary and Confidential

BOMARIN	270-201 – Amendment 5	Page 28
---------	-----------------------	---------

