8 STUDY OBJECTIVES

The primary objectives of the study are:

- To assess the safety of a single intravenous administration of a recombinant AAV5 encoding human coagulation FVIII (AAV5-hFVIII-SQ) vector.
- To determine the dose of AAV5-hFVIII-SQ required to achieve expression of hFVIII at or above 5% of normal activity (≥5 IU/dL) at 16 weeks after infusion. The kinetics, duration and magnitude of AAV-mediated hFVIII activity in individuals with haemophilia A will be determined and correlated to an appropriate BMN 270 dose.

The secondary objectives of the study are:

- To describe the immune response to the hFVIII transgene product and AAV capsid proteins following systemic administration of AAV5-hFVIII-SQ
- To assess the impact of BMN 270 on the frequency of FVIII replacement therapy during the study
- To assess the impact of BMN 270 on the number of bleeding episodes requiring treatment during the study

BOMARIN	270-201 – Amendment 5	Page 32
---------	-----------------------	---------

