9.2 Discussion of Study Design, Including Choice of Control Group

Study 270-201 is designed to be a first-in-man, phase 1/2 open-label, dose escalation study in patients with severe haemophilia A. Four doses of BMN 270 will be evaluated and the dose escalation decision tree for Cohorts 1-3 is summarized in Figure 9.1.1.

The decision to escalate to the next dose level will be made based on the review of safety parameters and FVIII activity by the Sponsor and the DRB.

There will be no control group. Parameters for each subject will be compared to a pre-treatment assessment of safety (liver function) and efficacy (number of bleeds, use of replacement therapy).

As AAV based treatment always leads to anti-capsid immune response, no true control group (for example with an empty AAV) is possible.

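### For subjects on prophylaxis before infusion, part of the reduction in factor use counted as efficacy is imposed by the protocol, and results are summarised by dose cohort without regard to prior regimen

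*Protocol*

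**What the plan says.** Section 8 lists two relevant secondary objectives: "To assess the impact of BMN 270 on the frequency of FVIII replacement therapy during the study" and "To assess the impact of BMN 270 on the number of bleeding episodes requiring treatment during the study". Section 9.7.3 turns them into measures: "Secondary efficacy measures will be the reduction in the frequency of factor replacement therapy, and reduction in the number of bleeding episodes".

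The comparator is in section 9.2. There is no control group, and "Parameters for each subject will be compared to a pre-treatment assessment of safety (liver function) and efficacy (number of bleeds, use of replacement therapy").

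Section 9.4.8.1 treats the two prior regimens differently. On-demand subjects carry on as before. For the others, "Subjects on prophylactic FVIII therapy will discontinue their treatment starting the day of infusion and switch to an" on-demand schedule. The same section collects prior FVIII use for the 6 months before enrolment, where it can be obtained. Inclusion criterion 3 in section 9.3.1 admits both regimens.

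Section 14.3 (Amendment 6; numbered 14.2 in Amendment 5) makes the analysis descriptive, summarises efficacy by dose cohort at each time point, and examines dose against efficacy. Neither 9.7.3 nor 14.3 mentions prior regimen.

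Sections 7 to 9 are quoted from Amendment 5, because that part of Amendment 6 is not in the extract. The Amendment 6 table of text revisions lists no change to 8, 9.2, 9.4.8.1 or 9.7.3.

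**The concern.** A prior-prophylaxis subject's baseline consists mainly of scheduled infusions. From Day 1 those are withdrawn by instruction, whether or not the vector works. A before-and-after difference then contains the effect of the instruction plus any effect of BMN 270, and with no control group the measure as defined cannot separate them. The objective nevertheless attributes the change to BMN 270.

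The bleed count moves the other way. Stopping prophylaxis would be expected to raise bleeds in the same subjects if the vector did nothing, so that measure is biased against the product. On-demand subjects have neither bias.

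A cohort summary that mixes the two groups therefore depends partly on how many subjects in that cohort came from prophylaxis. The cohorts are very small: the Amendment 4 rationale reports 9 subjects dosed, 7 of them at 6E13 vg/kg, which leaves 2 across the other doses then open. One subject's prior regimen could shift a cohort's figure and the apparent dose relationship.

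**Working it through.** The protocol states no expected reduction for this measure, so there is no figure to reproduce. The check is the change that would be seen with zero drug effect.

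**Inputs**
- Prophylaxis frequency, w: section 7.3 gives "both as prophylaxis 2-4 times per week". The Amendment 5 synopsis gives 2-3.
- On-demand bleeds per year, b: section 7.3 gives "up to 30 to 50 episodes/year for on demand treatment". The same sentence gives a mean of 1 to 7 on prophylaxis.
- Infusions per treated bleed, k: not in the documents; assumed 1, 2 or 3.

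**Formula for a prior-prophylaxis subject**

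Reduction = 1 − (b × k) / (w × 52).

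Baseline: 2 × 52 = 104 to 4 × 52 = 208 infusions a year. Infusions for breakthrough bleeds on prophylaxis are left out of the baseline; including them would make the reduction somewhat larger.

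| k | Smallest reduction (w = 2, b = 50) | Largest reduction (w = 4, b = 30) |
|---|---|---|
| 1 | 1 − 50/104 = 52% | 1 − 30/208 = 86% |
| 2 | 1 − 100/104 = 4% | 1 − 60/208 = 71% |
| 3 | 1 − 150/104 = −44% (an increase) | 1 − 90/208 = 57% |

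**Sensitivity**
- With the synopsis maximum of 3 infusions a week (156 a year), the upper ends become 1 − 30/156 = 81%, 1 − 60/156 = 62% and 1 − 90/156 = 42%.
- The artefact is zero when k = 52w/b, which runs from 104/50 = 2.1 to 208/30 = 6.9 infusions per bleed.
- The bleed rate is an upper figure, and a lower one enlarges the artefact. At 12 bleeds a year (the entry minimum for on-demand subjects) it runs from 1 − 36/104 = 65% (k = 3) to 1 − 12/208 = 94% (k = 1).

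**On-demand subjects.** Their regimen does not change, so the built-in reduction is 0%.

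**A mixed cohort.** With a fraction f on prior prophylaxis, the pooled reduction is 1 − bk / [f × 52w + (1 − f) × bk]. For f = 0.5, w = 3, b = 40:
- k = 1: 1 − 40/(78 + 20) = 59%
- k = 2: 1 − 80/(78 + 40) = 32%

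With f = 0 the pooled figure is 0%, so the regimen mix alone moves it.

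**Bleeds over the same switch.** The protocol's rates go from 1-7 to as many as 30-50 a year, at least 30/7 = 4.3-fold at those figures.

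**The case against.** The best defence has four parts.

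1. The two measures are paired. A prior-prophylaxis subject with no drug effect would show bleeds rising while factor use falls, which exposes the artefact. That is true, but only if the measures are read together within prior regimen. A cohort average that includes on-demand subjects blurs both signals.
2. Efficacy does not rest on factor use. The primary efficacy variable is central-laboratory FVIII activity (9.7.2), and everything is descriptive in up to 15 subjects. This stands, and it limits the consequence to interpretation of two secondary measures; no error rate is affected.
3. Tables by prior regimen can be left to the SAP, and 14.3 does not forbid them. Layout can be left there. The measure, the comparator and the mandated switch are fixed in the protocol, and a table layout does not change what 9.7.3 counts as efficacy.
4. A subject without benefit may go back to usual FVIII therapy, which the washout note in section 12.5.1 foresees. This stands: resumption would shrink the artefact, and the annual figures above assume none.

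Three stronger readings are tempting, but the documents do not support them. A reader might infer that a large reduction is bound to appear without drug effect; the sign can reverse at three infusions per bleed, and the documents do not say how many are used. A reader might see a conflict between the 6-month FVIII-use history and the 12-month bleed count; the latter is an eligibility criterion for on-demand patients (9.3.1), not an analysis baseline. A reader might conclude that factor use says nothing about efficacy in prior-prophylaxis subjects; it remains informative if the mandated stop is stated and bleeds are read beside it.

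**Conclusion.** The point holds for subjects on prophylaxis before infusion. For them the section 9.7.3 measure, with the section 9.2 comparator, mixes a protocol-imposed fall with any effect of BMN 270, and a substantial reduction can appear with no effect at all. The direction and mechanism follow from the protocol; the size does not follow firmly, because it rests on an assumed number of infusions per bleed, on rates quoted as upper figures, and on no return to usual therapy. The opposite bias in the bleed count and the dose-cohort summary make each cohort's result depend on its mix of prior regimens.

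A smaller wording fault goes with it: the objective in section 8 counts bleeds that need treatment, while 9.7.3 counts bleeding episodes without that limit.

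This should be corrected, but it does not undermine the primary efficacy variable.

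**What to change.** In sections 9.7.3 and 14.3:
- Report FVIII use and bleeds separately by prior regimen, prophylaxis or on-demand, in addition to dose cohort.
- For prior-prophylaxis subjects, state that the change in FVIII use includes the protocol-mandated stop of prophylaxis. Interpret it only together with the annualised bleed rate, set against each subject's own rate on prophylaxis.
- Use one bleed definition in sections 8 and 9.7.3.

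This is a change of wording and tabulation; it alters no treatment. The costs are very small subgroups within cohorts and a less favourable headline figure for FVIII use. The comparison also depends on pre-treatment history: FVIII use is collected only where it can be obtained, and the screening record of bleeds in section 12.2 states no period, so some subjects may lack a usable on-prophylaxis rate.
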